5.4 Visit Windows for Analysis

All efficacy and safety data will be summarized by week or by a duration of multiple weeks based on windows defined by study days, wherever applicable. An assessment for a subject will be classified according to the study day of the assessment and its corresponding analysis visit window (see Appendix 20.1 Analysis Visit Windows).

For the primary, secondary, and other efficacy endpoints, windows of multiple weeks are defined based on ranges of study days. Median, mean assessments, or annualized values from these windows may be used in efficacy analyses as deemed appropriate (see Section 13).

For the tertiary efficacy endpoints and the safety endpoints such as liver function tests and vital signs, the windows are designated for each scheduled week of visit and centered on a target day; for example, the target day for a Week 4 visit is Study Day 29. If there are two or more assessments within a designated window, the assessment that is closest to the target day will be used for analyses. If the two closest assessments to the target day are equidistant from the target day, then the mean of the two assessments will be used for analyses unless otherwise specified.

Appendix 20.1 Analysis Visit Windows lists the weeks assigned for the analyses of the clinical endpoint assessments and the corresponding range of treatment days (window) during which a visit may have occurred by analysis parameter.

5.5 Baseline Value

The baseline values of the annualized utilization of exogenous FVIII replacement therapy and the annualized number of bleeding episodes are calculated using the 12-month historical data prior to 270-303 study screening up until the BMN 270 infusion date.

An imputed baseline FVIII activity of 1 IU/dL will be used for the change from baseline analysis since there will be no washout of severe hemophilia A subjects' usual FVIII prophylaxis (in order to avoid increasing the risk of bleeding) prior to BMN 270 infusion.

The baseline values of other assessments are defined as the last available measurement prior to the administration of BMN 270 unless otherwise specified.

5.6 Handling of Dropouts and Missing Data

If a subject withdraws from the study prematurely, the subject will be asked to complete an Early Termination Visit (ETV), the data from which will be included in summaries and analyses.

Missing dates or partially missing dates will be imputed conservatively for concomitant medications and adverse events (AEs) to ensure that an AE is considered treatment emergent when possible and the duration is the longest possible duration.

FVIII activity levels below the lower limit of quantitation (LLoQ) will be imputed as 0 IU/dL. To reduce variation caused by random fluctuation, FVIII activity will be analyzed as the median of observed values within each analysis visit window as defined in Appendix 20.1. Missing FVIII activity values will be imputed as follows.

- Dropout missing:
For subjects who discontinue from the study early, missing FVIII activity values post-discontinuation will be imputed to be 0 IU/dL through the data cutoff date for the analysis.
- Intermittent missing:
For subjects who continue the study, missing FVIII activity values (e.g., due to a missed study visit) will be imputed to be the smaller of the last prior non-missing value and the next non-missing value. In rare cases where the next value is unavailable for a subject who did not drop out, the missing value will be imputed through linear extrapolation using the last two prior non-missing values, capped at the last non-missing value.

Other missing data imputation for the primary efficacy endpoint and the secondary efficacy endpoints are specified in the corresponding analysis sections.

Other missing data will not be imputed unless otherwise stated.

6 SUBJECT DISPOSITION

The number of subjects screened, number and percentage of screen failures by screen failure reasons will be summarized for all subjects screened. Subjects are considered enrolled into the study if the Baseline visit was completed, and the enrollment date is defined as the Baseline visit date. The number of subjects enrolled and the number and percentage by reason for subjects enrolled but not treated will be provided. Inclusion in and exclusion from analysis populations, as well as reason for exclusion, will be summarized for all subjects enrolled.

7 DISCONTINUATION AND COMPLETION

For treated subjects who prematurely discontinue study participation prior to the Week 52 visit or during the long-term follow-up period, the primary reason for discontinuation will be summarized for the ITT population. The number and percentage of subjects who are continuing the study at the data cutoff date for the 1-year analysis and subjects who completed Week 52 visit will also be provided for all treated subjects.

8 PROTOCOL DEVIATIONS

The trial's Study Specific Guideline for Managing Protocol Deviations defines protocol deviations, including whether they are minor or major. Major protocol deviations will be summarized. A data listing of protocol deviations will be provided as well.

9 DEMOGRAPHICS AND BASELINE CHARACTERISTICS

Subject demographic and baseline characteristics to be summarized include

- age at enrollment (years)
- age group ($\geq 18 - < 65$, ≥ 65)
- age group ($\geq 18 - < 30$, $\geq 30 - < 50$, ≥ 50)
- sex (female/male)
- ethnicity
- race
- height (cm)
- weight (kg)
- BMI (kg/m^2)
- baseline ECG evaluation
- history of liver disease (Yes/No)
- history of hepatitis B (Yes/No)
- history of hepatitis C (Yes/No)
- history of HIV (Yes/No)
- baseline disease characteristics including
 - time since diagnosis of hemophilia A (years)
 - type of treatment for hemophilia A (FVIII prophylaxis or emicizumab)
 - history of FVIII inhibitor (Yes/No)
 - FVIII genotyping results
 - number of target joints
 - body location of target joints
 - ambulatory assist device requirement (Yes/No)
- baseline FVIII activity (IU/dL) including values within 72 hours after a FVIII infusion
- baseline FVIII activity (IU/dL) excluding values within 72 hours after a FVIII infusion
- duration of baseline data collection periods (months)
- baseline annualized utilization (IU/kg/year) of exogenous FVIII replacement therapy

- baseline annualized number of FVIII infusions (infusions/year)
- baseline annualized bleeding rate (ABR) (treated bleeds/year)
- baseline ABR (all bleeds/year)

10 MEDICAL HISTORY

Medical history will be coded using the most current version of Medical Dictionary for Regulatory Activities (MedDRA) at the time of coding. Medical history will be summarized by system organ class (SOC) and preferred term (PT).

11 PRIOR AND CONCOMITANT MEDICATIONS/PROCEDURES

Prior and concomitant medications are defined as follows:

- Prior medication - any medication taken prior to the initiation of the investigational product (IP) and within 30 days prior to Screening
- Concomitant medication - any medication taken after the initiation of the IP

When a medication starts prior to the initiation of the IP and continues while on study, it will be summarized as both a prior and concomitant medication.

All medications will be coded using the current version of the World Health Organization Drug (WHO Drug) Dictionary.

Prior and concomitant medication use will be separately summarized by Anatomical Therapeutic Chemical (ATC) medication class (Level 4) and preferred name (i.e., generic medication name), and by NIH hepatotoxicity likelihood grades and preferred name as well. A subject reporting the same medication more than once will be counted once when calculating the number and percentage of subjects who received that medication.

Corticosteroid usage including total dose and total duration per subject, dose per corticosteroid course, duration per corticosteroid course, and number of corticosteroid courses will be summarized for therapeutic purposes. Compliance to protocol-specified 19-week prophylactic corticosteroid regimen will be summarized (e.g., the number and proportion of subjects who received protocol-recommended dose of prophylactic corticosteroids for > 90% of time in the first 19 weeks post BMN 270 infusion). Non-steroidal immunosuppressants may be summarized as well.

Baseline FVIII prophylaxis treatment will be summarized by type (extended half-life, standard half-life, or plasma derived) and drug preferred name.

12 EXTENT OF EXPOSURE TO STUDY DRUG

Each subject will receive a single intravenous infusion of BMN 270, and the volume of infusion will depend on the subject's weight. Actual dose (vg/kg), duration of infusion, initial and overall rate of infusion for each subject will be summarized descriptively. Investigational product dosing compliance will be assessed by providing descriptive summaries of actual dose, number and percentage of subjects with administered IP infusions below the planned dose, subjects with dose changes, and various reasons of dose changes. The post-BMN 270 follow-up time of each subject will be summarized descriptively.

A data listing of drug exposure will be provided.

13 EFFICACY EVALUATIONS

This section describes the analyses to be undertaken for the primary, secondary, and other efficacy variables as described in the protocol.

13.1 Efficacy Evaluation Periods

To avoid breakthrough bleeding, subjects only discontinued exogenous prophylactic FVIII replacement therapy after 4 weeks following infusion of BMN 270. Four weeks represents the time by which endogenous production of FVIII following gene transfer is expected to be efficacious, based on earlier results.

For the primary data analysis, the efficacy evaluation period for

- Efficacy endpoints such as ABR (all bleeds and treated bleeds), number of bleeds (all bleeds and treated bleeds), annualized FVIII utilization, annualized FVIII infusions and PROs: will be defined as starting from Week 5 post-BMN 270 infusion (Study Day 33) or the end of FVIII prophylaxis plus the washout period (3 days for products of standard half-life or plasma-derived and 5 days for products of extended half-life), whichever is later, until subjects complete the study, reach the last visit by data cutoff for the analysis, or withdraw from the study (ETV), whichever is the earliest
- Efficacy endpoint of FVIII activity based on chromogenic substrate assay: will be defined as starting from Week 5 post-BMN 270 infusion (Study Day 33) until subjects complete the study, reach the last visit by data cutoff for the analysis, withdraw from the study (ETV) (FVIII activities post withdrawal will be imputed to be 0 IU/dL through the data cutoff date for the analysis), or resume routine FVIII prophylaxis (should that occur) (restart of FVIII prophylaxis is defined as the first usual FVIII prophylaxis administered at least once a week for ≥ 4 consecutive weeks), whichever is the earliest
- Efficacy endpoint of FVIII activity based on one-stage assay: will be defined as starting from Week 5 post-BMN 270 infusion (Study Day 33) until subjects complete the study, reach the last visit by data cutoff for the analysis, resume routine FVIII prophylaxis or start emicizumab prophylaxis (should that occur) (start of emicizumab prophylaxis is defined as the first emicizumab injection among 2 or more emicizumab injections administered within 31 days), whichever is the earliest.

For supportive data analyses, the efficacy evaluation period for

- Efficacy endpoint of FVIII activity: will be defined as from BMN 270 infusion to until subjects complete the study, reach the last visit by data cutoff for the analysis, or withdraw from the study (ETV), whichever is the earliest

- Efficacy endpoints such as ABR, number of treated bleeds, annualized FVIII utilization, annualized FVIII infusions: will be some of the efficacy evaluation periods listed in [Table 13.1.1](#). In addition, descriptive summary will be provided in Weeks 1-4 and Week 1-end of FVIII prophylaxis (defined as end of week 4 post-BMN 270 infusion or end of FVIII prophylaxis plus 2 days for products of standard half-life or plasma-derived and 4 days for products of extended half-life, whichever is later)

Time to discontinuation of FVIII prophylaxis post-BMN 270 infusion and duration of efficacy evaluation period for primary analysis of the aforementioned efficacy endpoints will be summarized.

Table 13.1.1: Efficacy Evaluation Periods for the Analyses of Number of Bleeding Episodes, FVIII Utilization and FVIII Infusions

Efficacy Evaluation Period	Start Point	End Point	Analysis
Post-FVIII prophylaxis period	Start of Week 5 post-BMN 270 infusion or end of FVIII prophylaxis plus 3 days for products of standard half-life or plasma-derived and 5 days for products of extended half-life, whichever is later	Last visit by data cutoff	Primary, Wilcoxon signed-rank test
Post-FVIII prophylaxis – week 52	Start of Week 5 post-BMN 270 infusion or end of FVIII prophylaxis plus 3 days for products of standard half-life or plasma-derived and 5 days for products of extended half-life, whichever is later	Last visit by data cutoff or end of Week 52 post-BMN 270 infusion, whichever is earlier	Supportive, Wilcoxon signed-rank test
Post-FVIII prophylaxis – restart of prophylactic treatment up to Week 52	Start of Week 5 post-BMN 270 infusion or end of FVIII prophylaxis plus 3 days for products of standard half-life or plasma-derived and 5 days for products of extended half-life, whichever is later	Last visit by data cutoff, end of Week 52 post-BMN 270 infusion or 1 day before restart of prophylactic treatment, whichever is earlier	Supportive, Wilcoxon signed-rank test
Post-FVIII prophylaxis – restart of prophylactic treatment up to last visit	Start of Week 5 post-BMN 270 infusion or end of FVIII prophylaxis plus 3 days for products of standard half-life or plasma-derived and 5 days for products of extended half-life, whichever is later	Last visit by data cutoff or 1 day before restart of prophylactic treatment, whichever is earlier	Supportive, Wilcoxon signed-rank test

Note: end of FVIII prophylaxis is defined as last usual FVIII prophylaxis not followed by another usual FVIII prophylaxis for at least 28 days.

Restart of prophylactic treatment means restart of FVIII or start emicizumab prophylaxis. Restart of FVIII prophylaxis is defined as the first usual FVIII prophylaxis administered at least once a week for ≥ 4 consecutive weeks. Start of emicizumab prophylaxis is defined as the first emicizumab injection among 2 or more emicizumab injections administered within 31 days.

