13.3.2 Haemo-QoL-A and Other Patient-Reported Outcomes

The following patient-reported outcomes (PROs) will be used to assess subjects' quality of life (QoL) during the study:

- Change from baseline in the total score of HAEMO-QoL-A at Week 52 of the study post-BMN 270 infusion
- Change from baseline in the EQ-5D-5L score at Week 52 of the study post-BMN 270 infusion

- Change from baseline in the Work Productivity and Activity Impairment plus Classroom Impairment Questions: Hemophilia Specific (WPAI+CIQ:HS) score at Week 52 of the study post-BMN 270 infusion
- Change from baseline in Patient Reported Outcomes, Burdens, and Experiences (PROBE) score at Week 52 of the study post-BMN 270 infusion

The PROs will be assessed at baseline, Week 4, Week 12, Week 26, Week 52 and every 6 months starting with Week 76 per protocol-scheduled assessments.

The QoL endpoints including the sub-scale/sub-domain scores (except for PROBE) will be summarized descriptively for the mITT population using the observed cases by visit up to the data cutoff. The p-value and 95% CI for the change from baseline based on two-sided t-test will be provided for descriptive purposes. PROBE will be analyzed externally through a separate statistical analysis plan.

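### SAP Section 13.1 puts PROs in the post-FVIII-prophylaxis period, contradicting the by-visit PRO analysis, with its Day 29 visit, in Section 13.3.2 and Appendix 20.1

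*SAP*

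**What the plan says.** Two parts of the current SAP (version 2.0) decide which PRO records count, and they differ.

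**Section 13.1.** For the primary data analysis, one bullet groups PROs with ABR, bleed counts, FVIII utilization and FVIII infusions: "annualized FVIII infusions and PROs: will be defined as starting from Week 5 post-BMN 270 infusion (Study Day 33". The start moves later if prophylaxis ended later, with a washout of "3 days for products of standard half-life or plasma-derived and 5 days for products of extended half-life". The notes to Table 13.1.1 define the end of prophylaxis as the "last usual FVIII prophylaxis not followed by another usual FVIII prophylaxis for at least 28 days".

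**Section 13.3.2 and Appendix 20.1.** The PRO section sets the schedule: "The PROs will be assessed at baseline, Week 4, Week 12, Week 26, Week 52 and every 6 months starting with Week 76". The scores are "summarized descriptively for the mITT population using the observed cases by visit up to the data cutoff", and no condition on stopping prophylaxis is attached. Appendix 20.1 gives PROs fixed windows: Week 4 is Days 6 to 57 (target Day 29) and Week 52 is Days 275 to 448 (target Day 365). Section 5.4 confirms that "the target day for a Week 4 visit is Study Day 29".

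The SAP gives no order of precedence. The Section 13.1 bullet has the same content in version 1.0.

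**The concern.** A score taken at a scheduled visit has been given the evaluation period of endpoints that are counted over time. That period opens after the first scheduled post-infusion PRO visit, so two programmers working from different sections would produce different Week 4 tables. Later tables could differ too, because Section 13.1 makes inclusion depend on when each subject stopped prophylaxis. The SAP treats that date as variable, since Section 13.1 plans a summary of time to discontinuation.

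Stopping prophylaxis is itself a consequence of how well treatment worked, so a rule that admits PRO data only after stopping selects on a post-treatment outcome. The PRO analysis also has no safety net. Section 13.3.1 imputes a missing post-baseline change for ABR and FVIII utilization, whereas PROs use observed cases and Section 5.6 leaves other missing data unimputed. Haemo-QoL-A at Week 52 is a secondary objective, so the rule for which records enter should be unambiguous.

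**Working it through.** No sample-size or power figure bears on this point. The check is day arithmetic on the two rules.

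**Inputs**
- Period start under Section 13.1: S = max(33, E + w), where E is the day prophylaxis ended and w is 3 days (standard half-life or plasma-derived) or 5 days (extended half-life).
- PRO targets and windows from Appendix 20.1: Week 4, Day 29, Days 6 to 57; Week 12, Day 85; Week 52, Day 365, Days 275 to 448.

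A PRO on day d is inside the Section 13.1 period only if d ≥ 33 and E ≤ d − w.

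**Week 4**
- On-time visit: 33 − 29 = 4, so Day 29 precedes the earliest possible start by 4 days and is outside for every subject.
- Window length: 57 − 6 + 1 = 52 days.
- Always outside: Days 6 to 32, which is 33 − 6 = 27 days (27/52 = 52%).
- Possibly inside: Days 33 to 57, which is 57 − 33 + 1 = 25 days, and only if prophylaxis plus washout has also ended. Even on Day 57 this needs E ≤ 54 (w = 3) or E ≤ 52 (w = 5).

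**Later visits: latest end of prophylaxis that keeps the record inside**

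| PRO taken on | w = 3 | w = 5 |
|---|---|---|
| Day 85 (Week 12 target) | Day 82 | Day 80 |
| Day 365 (Week 52 target) | Day 362 | Day 360 |
| Day 448 (end of Week 52 window) | Day 445 | Day 443 |

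**No end of prophylaxis.** A subject without the required 28-day gap has no E and therefore no S. Read literally, none of that subject's PROs would fall in a Section 13.1 period.

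**The same records under Section 13.3.2 and Appendix 20.1.** All of them are included, whatever E is.

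**Which rule fits the rest of the SAP**
- Every other endpoint in the Section 13.1 bullet is a count or an amount accumulated over a period.
- The title of Table 13.1.1 covers bleeding episodes, FVIII utilization and FVIII infusions, not PROs.
- Appendix 20.1 ties those endpoints to the post-prophylaxis period and gives PROs ordinary visit windows.
- The objectives attach the evaluation period to FVIII use and bleeds; the Haemo-QoL-A objective says only Week 52.

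All four point to the PRO entry in Section 13.1 being misplaced.

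**The case against.** The strongest reply is that the PRO-specific text already settles the matter. Section 13.3.2 and the synopsis describe a by-visit, observed-case summary in the mITT population, and Appendix 20.1 supplies the windows. On that view Section 13.1 contains a stray phrase that nobody would apply. The PRO endpoints are changes at Week 52, Week 4 is only a descriptive time point, and the p-values and confidence intervals are labelled descriptive.

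Most of this stands, and it limits the severity. It does not remove the contradiction: Section 13.1 names PROs explicitly, under the primary data analysis, and nothing says that it yields to Section 13.3.2.

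A reader might go further and infer that the plan does drop subjects who never stop prophylaxis from the Week 52 analysis, and so biases Haemo-QoL-A toward benefit. The documents do not support that. No such subject is reported, and Section 13.1 says in the past tense that "subjects only discontinued exogenous prophylactic FVIII replacement therapy after 4 weeks following infusion of BMN 270". Section 13.1 gives a subject with no end of prophylaxis no start date; it does not say that the subject is removed, and Section 13.3.2 would keep the observed value. A bias would also require those subjects' mean change to differ from that of the others, on which the SAP has no figures. Its size cannot be estimated, since the number of subjects in the mITT population is not given either.

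**Conclusion.** The point holds as an internal contradiction of low severity. If Section 13.1 is applied literally, every on-time Week 4 PRO is outside the evaluation period, as are all records from Days 6 to 32. Records from Days 33 to 57 count only once prophylaxis plus washout has ended. Section 13.3.2 and Appendix 20.1 include all of them.

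At Week 52 the conflict is conditional. A PRO taken on Day 365 is affected only in a subject who never stopped prophylaxis, or who stopped after Day 362 (3-day washout) or Day 360 (5-day washout). Without such a subject, the on-time Week 52 result is the same under either rule. Exclusion at Week 4 should not be read as the plan's settled intention, nor bias at Week 52 as established. No confirmatory test depends on this.

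**What to change.** Delete the words *and PROs* from the first Section 13.1 bullet, and add one sentence there or in Section 13.3.2: PROs are analysed for all subjects in the analysis population (mITT) by the Appendix 20.1 visit windows, regardless of FVIII prophylaxis status. Naming the population keeps the sentence consistent with Section 13.3.2 and the synopsis.

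The cost is two words removed and one sentence added. Sample size, power, the primary analysis and data collection do not change.

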13.2 Primary Efficacy Endpoint

The primary efficacy endpoint is:

- The change from baseline (assuming no treatment for severe hemophilia A) in FVIII activity, as measured by chromogenic substrate assay, at Week 52 (during Weeks 49 - 52) post-BMN 270 infusion

Each subject's FVIII activity level at Week 52 is defined as the median of the values obtained within the analysis window at Weeks 49-52 as defined in Appendix 20.1. The baseline value will be imputed as 1 IU/dL, since there will be no washout of severe hemophilia A subjects' usual FVIII prophylaxis (in order to avoid increasing the risk of bleeding) prior to BMN 270 infusion. Post-BMN 270 infusion values for FVIII activity will be excluded from analysis if obtained within 72 hours (or 3 calendar days if time is not available) since the last infusion of exogenous FVIII replacement therapy.

The change from baseline in the FVIII activity at Week 52 post-BMN 270 infusion will be tested using a one-sample t-test. The hypotheses are:

H_0 (null hypothesis): Change = 0 versus H_1 (alternative hypothesis): Change \neq 0.

Only positive changes indicate efficacy.

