13.2.2 Supportive and Sensitivity Analyses for the Primary Efficacy Endpoint

The FVIII activity level will be summarized descriptively in 4-week or 6-week analysis visit windows with missing data imputed from baseline up to the last possible visit by the data cutoff for the 1-year analysis. The visits and analysis visit windows are defined in Appendix 20.1 Analysis Visit Windows. Each subject's FVIII activity level in an analysis visit window is defined as the median of the values obtained within the window. The number and proportion of subjects achieving FVIII activity level per chromogenic assay of < LLoQ (3 IU/dL), between levels of \geq LLoQ (3 IU/dL) - < 5 IU/dL, between the levels of \geq 5 - < 15 IU/dL, between the levels of \geq 15 - < 40 IU/dL, between the levels of \geq 40 - \leq 150 IU/dL, and > 150 IU/dL will also be summarized every 4 or 6 weeks post-BMN 270 infusion up to data cutoff. The number and proportion of subjects whose FVIII activity is < 5, \geq 5 - < 40 and \geq 40 IU/dL will also be provided.

Boxplots of median FVIII activity values using chromogenic substrate assay by 4-week or 6-week windows (Appendix 20.1 Analysis Visit Windows) over time will be provided.

The 4-week or 6-week analysis will be repeated using efficacy evaluation period for supportive analysis of FVIII activity without imputation for the mITT population.

The maximum of each subject's FVIII activity levels (medians of the values in analysis visit windows defined in Appendix 20.1), and the time to the maximum level, will be summarized descriptively. The number and proportion of subjects whose maximum FVIII activity level is < LLoQ (3 IU/dL), between levels of \geq LLoQ (3 IU/dL) - < 5 IU/dL, between the levels of \geq 5 - < 15 IU/dL, between the levels of \geq 15 - < 40 IU/dL, between the levels of \geq 40 - \leq 150 IU/dL, and > 150 IU/dL will also be summarized.

The primary and supportive analyses described above may be conducted for FVIII activity levels measured by one-stage clotting assay.

To investigate the relationship between the FVIII activity values by one-stage clotting and chromogenic substrate assays, a linear regression to fit a line to the observed values by these two assays will be conducted for the mITT population.

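### The supportive FVIII-activity period and the one-stage versus chromogenic regression do not carry over the emicizumab stop that Section 13.1 sets for the one-stage assay

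*SAP*

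**What the plan says.** The text is that of SAP version 2.0. Version 1.0 has the same rules, with ITT in place of mITT.

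- **Primary period, chromogenic assay (Section 13.1).** Apart from completion, last visit and withdrawal, the one treatment-related stop is a return to routine FVIII prophylaxis: "or resume routine FVIII prophylaxis (should that occur) (restart of FVIII prophylaxis is defined as the first usual FVIII prophylaxis". Emicizumab does not end this period.
- **Primary period, one-stage assay (Section 13.1).** This period ends when subjects "resume routine FVIII prophylaxis or start emicizumab prophylaxis (should that occur", with emicizumab start defined by repeated injections within a fixed interval.
- **Supportive period (Section 13.1).** There is one definition without an assay split: "Efficacy endpoint of FVIII activity: will be defined as from BMN 270 infusion to until subjects complete the study". Last visit by cutoff and withdrawal are the other end points.
- **Use of the supportive period (Section 13.2.2).** The 4-week or 6-week window analysis "will be repeated using efficacy evaluation period for supportive analysis of FVIII activity without imputation for the mITT population".
- **Extension to the one-stage assay (Section 13.2.2).** This is optional: "The primary and supportive analyses described above may be conducted for FVIII activity levels measured by one-stage clotting assay".
- **Assay comparison (Section 13.2.2).** This is a commitment: "a linear regression to fit a line to the observed values by these two assays will be conducted for the mITT population".
- **Value-level exclusion (Section 13.2).** Post-infusion FVIII values are "excluded from analysis if obtained within 72 hours (or 3 calendar days if time is not available) since the last infusion of exogenous FVIII". Emicizumab is not mentioned.

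**The concern.** An emicizumab stop that applies to one assay only is hard to explain unless the authors regard one-stage readings after that point as not valid for the FVIII-activity endpoint. The same reasoning should then apply wherever one-stage values are summarised or compared with chromogenic values. As written, it does not apply to the supportive period, and no rule applies it to the regression.

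The SAP treats a post-infusion emicizumab start as a real possibility. It defines the event, and Table 13.1.1 includes supportive bleeding and utilization periods that end the day before it. The supportive FVIII-activity period has no matching rule. It also runs to the last visit by cutoff, not only to Week 52, so late starts can fall inside it.

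At stake are the line relating the two assays and any one-stage supportive summary. Both could include readings that the one-stage version of the primary analysis would leave out, and a reader of the report would not know.

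**Working it through.** The plan states no figure on this point, so there is none to reproduce. The check is a comparison of rules, followed by simple algebra for what an affected value would do.

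**Step 1. Which rule removes a one-stage value taken after emicizumab start?**

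| Analysis | Status in the SAP | Stops at resumed FVIII prophylaxis? | Stops at emicizumab start? |
|---|---|---|---|
| Chromogenic, primary period | Planned | Yes | No |
| One-stage, primary period | Optional | Yes | Yes |
| Chromogenic, supportive period | Planned | No | No |
| One-stage, supportive period | Optional | No | No |
| One-stage versus chromogenic regression | Planned | Not stated | Not stated |

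The 72-hour rule is the only value-level exclusion. It still gives some protection against resumed FVIII when the supportive period drops the FVIII-prophylaxis stop. It gives none against emicizumab. The last two rows therefore have no rule that takes these values out.

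**Step 2. When can this occur?** Section 4.1 notes that no subject was on emicizumab before BMN 270. Only starts after infusion matter, and Section 13.1 treats them as something that may or may not happen.

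**Step 3. Effect on a window mean.** Let k be the number of starters with an observed value in the window, S the shift in each one-stage reading, and n the number of observed subjects.

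Change in mean = k × S / n.

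The SAP gives none of these three. The number treated is 22 (Section 4.2), which is an upper limit for n, because the repeat analysis uses observed mITT subjects and the mITT size is not stated. The values of k and S below are assumptions, shown as a range with n = 22:

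| Shift S (IU/dL, assumed) | k = 0 | k = 1 | k = 2 |
|---|---|---|---|
| 10 | 0 | 10/22 = 0.45 | 20/22 = 0.91 |
| 50 | 0 | 50/22 = 2.27 | 100/22 = 4.55 |
| 100 | 0 | 100/22 = 4.55 | 200/22 = 9.09 |

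A smaller n makes each entry larger in proportion.

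**Step 4. Effect on the regression.** Take chromogenic as x and one-stage as y, with N pairs, of which m are shifted by S. Let x̄ be the mean chromogenic value and Sxx the sum of squared deviations of x from x̄. Compared with the same pairs unshifted, least squares gives:

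- change in slope = S × Σ(x_j − x̄) / Sxx, summed over the m affected pairs;
- change in intercept = m × S / N − x̄ × (change in slope).

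If the affected pairs lie below x̄ and S is positive, the slope falls and the intercept rises. Section 5.6 sets chromogenic values below the LLoQ to 0, so a starter who had lost expression would lie at the low end of x. That starters would be such subjects, and that the shift would be upward, are both assumptions; the SAP says neither. The SAP gives no x̄, Sxx, m or S, so no numerical distortion can be derived for this trial.

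**The case against.** The strongest reply is that a supportive period is meant to differ from the primary one. This one also begins at infusion rather than Day 33 and drops the FVIII-prophylaxis stop, so it can be read as a deliberately inclusive display without imputation. Omitting a primary stop there is not in itself a contradiction. That is fair for the chromogenic assay. It is weaker for the one-stage assay, because the emicizumab stop is the one treatment-related rule that Section 13.1 makes assay-specific, and nothing says that it was dropped on purpose.

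Four further points stand and limit the concern:

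- The SAP never says that emicizumab interferes with the one-stage assay, and never calls such readings unusable. A reader might infer both. The text supports only the implication drawn from a stop that applies to one assay.
- The one-stage supportive summaries are optional, and the boxplots over time are specified for the chromogenic assay only.
- The regression is silent on period. It would include these values because no restriction is stated, not because the SAP says that they belong. The SAP gives its purpose as investigating the relationship between the assays. It converts no result from one assay to the other, and no endpoint depends on the line.
- The number of starters may be zero.

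**Conclusion.** The gap is real but minor. Section 13.1 applies an emicizumab stop to the one-stage assay in the primary period. The supportive period does not repeat it, the regression states no restriction, and the 72-hour rule does not cover it. Followed literally, the planned regression and any one-stage supportive summary would take in values that the SAP's own one-stage rule leaves out, if any subject starts emicizumab after BMN 270.

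The size is unknown. It is k × S / n for a mean and nil if k = 0. The figures shown for k = 1 and k = 2 rest on assumed shifts and on n = 22, and they are not estimates for this trial.

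A reader might go further and conclude that signal from another drug will be reported as FVIII from the transgene. The documents do not support that. They state no interference, no direction or size of shift, and no actual starter. The primary chromogenic endpoint and its t-test do not use one-stage values. The secondary endpoints (FVIII utilization, bleeding rates and Haemo-QoL-A) do not use FVIII activity. None of these changes.

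**What to change.** - **Section 13.1:** split the supportive FVIII-activity period by assay. Leave the chromogenic period as it is. End the one-stage period at the start of emicizumab prophylaxis, using the definition that the SAP already contains.
- **Section 13.2.2:** restrict the one-stage versus chromogenic regression to paired samples taken before any emicizumab start.
- **Listing:** show later one-stage values separately, flagged, so that nothing is hidden.

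The cost is about two sentences of SAP text and one filter in the programs. The downside is that some late one-stage values are lost from these summaries for any subject who starts emicizumab. If the authors do want them in the inclusive summary, one sentence saying so, with the values flagged, would also remove the ambiguity.
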